## **6.7 Concomitant Medications and Procedures and Other Restrictions**

### **6.7.1 Concomitant Medications and Procedures**

Any medication taken by a subject from 30 days prior to the screening visit through the first 43 days of the study and the reason for its use will be documented.

Previous prescription medication for mild chronic health disorders (eg, hypertension or hypercholesterolemia) or maintenance (eg, contraception) will be allowed at the discretion of the Investigator as long as the subject has been on a stable dose for at least 3 months. Subjects should continue their regular maintenance medications throughout study participation unless instructed to discontinue or change by the Investigator or their personal physician. If concomitant medications are discontinued by a subject during study conduct the subject should notify the Investigator. Subjects should refrain from starting new medications, modifying current concomitant medications, or receiving vaccinations during study participation unless prescribed by the Investigator for treatment of specific clinical events.

Subjects should not receive any vaccine within 1 month before screening.

Subjects should not be using prescription medications for the prophylaxis of SARS-CoV-2.

Subjects should not participate or plan to participate in a study that involves an experimental agent (vaccine, drug, biologic, device, or medication); or should not have received an experimental agent within 1 month before enrollment in this study; or who expect to receive another experimental agent during participation in this study.

A positive drug screen result with a corresponding prescribed concomitant medication will be allowed if, in the opinion of the investigator and Medical Monitor, the concomitant medication does not make the subject unsuitable to participate in the clinical trial.

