## **2.4 Study Rationale**

Multiple vaccines have been approved for emergency use for the prevention of SARS-CoV-2, with other vaccines close to being available either through emergency use or licensed vaccines. Although work continues on antiviral treatments for SARS-CoV-2, given the crisis of COVID-19 infections in the world, the fast expansion to the US and other parts of the world, and the global push to vaccinate everyone, additional sources of effective vaccine will be needed.

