23. Individuals who plan to receive another vaccine within the first 3 months of the study except influenza vaccine which should not be given within 2 weeks of study vaccine.
24. Receipt of any other approved SARS-CoV-2 vaccine prior to the first study vaccine or within 90 days after administration of the first study vaccine.
25. Receipt of any other experimental coronavirus vaccine at any time prior to or during the study.
26. Receipt of any investigational vaccine or drug within 1 month of enrollment and through the end of the study (1 year after first vaccination).

27. Plan to travel outside the subjects' country of residence from enrollment through Day 43.
28. History of surgery or major trauma within 12 weeks of screening, or surgery planned during the study.
29. Significant blood loss (>450 mL) or has donated 1 or more units of blood or plasma within 6 weeks prior to study participation.
30. Strenuous activity (as assessed by the Investigator) within 48 hours prior to dosing (Days 1 and 22).
31. A positive urine drug screen without evidence of corresponding prescribed concomitant medication(s) at Screening. Note: A positive drug screen result with a corresponding prescribed concomitant medication will be allowed if, in the opinion of the investigator and Medical Monitor, the concomitant medication does not make the subject unsuitable to participate in the clinical trial. For a positive tetrahydrocannabinol result, refer to Exclusion Criteria #17.
32. Positive alcohol screen.
33. Positive screen for HIV-1 and HIV-2 antibodies, HBsAg, or HCV antibody.
34. Involved in the planning or conduct of this study.
35. Unwilling or unlikely to comply with the requirements of the study.
36. Subject is an employee, contractor, friend of or relative of any employee of Sponsor, CRO, study site or site affiliate.

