## **6.6.2            Blinding of Treatment Assignment**

ICON will maintain the randomization code in a secure location with controls to prevent unauthorized access, including the computer program written to generate the randomization, randomization codes, program log, seed number used by the program, copy of the randomization plan along with approval documentation as appropriate, and the write-protected electronic storage medium.

The site and CRO will name an unblinded statistician to provide the randomization code. The pharmacists will be unblinded. Since the placebo and vaccine will not be identical in appearance, the staff member administering the doses will be unblinded and will not participate in any additional study activities. In order to preserve the blind, study vaccine will be prepared and administered in a manner that masks the content for both the subject and any observers. Investigators, site staff, subjects, CRO [except for the unblinded team members preparing the data for unblinded iSRC review] will remain blinded until the completion of the study. The Sponsor will remain blinded to individual subjects' treatment assignment from the beginning of the study through Day 43. When the data is unblinded for the interim analysis after all subjects complete Day 43, the Sponsor will be unblinded.

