## **9 STATISTICAL CONSIDERATIONS**

The statistical analysis will be conducted following the principles as specified in ICH Topic E9 (CPMP/ICH/363/96).

All statistical analyses will be described in a separate SAP.

The statistical evaluation will be performed using SAS® software version 9.4 or higher (SAS Institute, Cary, NC). All data will be listed, and summary tables will be provided. No formal significance testing will be performed. Summary statistics will be presented by treatment group and include subset analysis (eg, all subjects, seronegative subjects [ie, neutralizing antibody titer < 10 at screening], seropositive subjects, and subjects that received an FDA Emergency Use Authorization/licensed COVID vaccine). For continuous variables, data will be summarized with the number of subjects, mean, standard deviation, median, minimum, maximum, geometric mean, CV%, GeoCV%, and 95% CI by treatment group. For categorical variables, data will be tabulated with the number and proportion of subjects for each category by treatment group.

The database will be locked and unblinded after the data have been monitored for all subjects through Day 43. Details of the unblinded interim analysis are presented in [Section 9.5](#).

The final analysis of the safety and immunogenicity data collected from Day 43 through Day 365/approximately 1 year after first vaccination will be performed after the study is completed. An addendum to the initial CSR will be prepared with data from final analysis. Details of the statistical analyses, methods, and data conventions will be described in the SAP.

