### **9.2 Analysis Populations**

Enrolled Population: All subjects who signed the ICF.

**Safety Population:** All subjects who provide consent, are randomized, and receive any amount of study vaccine/placebo. The Safety Population will be used for the demographic, baseline characteristic, safety data summaries, and the analysis of primary endpoints such as occurrence of solicited local and systemic reactogenicity.

**Per Protocol (PP) Population:** Includes all subjects in the Safety Population who receive the assigned doses of the study vaccine/placebo according to protocol, have serology results, and have no major protocol deviations affecting the primary immunogenicity outcomes, as determined by the Sponsor before database lock and unblinding. Subjects that are immunized with an approved vaccine will be captured as a subset analysis of the PP Population at Days 90, 181, 273, and 365 based on the date of receiving an approved COVID-19 vaccine.

**Modified Intent-to-Treat (mITT) Population:** Includes all subjects in the Safety Population who provide any serology data. The mITT Population will be used for the immunogenicity analysis.

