### **9.3 Randomization**

The overall randomization for the study will be 2:1 (active:placebo). Each Part (A and B) and treatment (low and high) will be randomized individually 2:1 (active to placebo).

The study will start with Part A (18-49 years) low dose, randomized in a 2:1 ratio (30 subjects active:15 subjects placebo) for Treatment A (15 µg TAP-COVID-19 vaccine + 0.5 mg CpG).

Part A (18-49 years) high dose will be randomized in a 2:1 ratio (30 subjects active:15 subjects placebo) for Treatment B (45 µg TAP-COVID-19 vaccine + 0.5 mg CpG) after Part A low dose has completed enrollment and the iSRC has reviewed safety and tolerability data through Day 8.

Part B (50-85 years) low dose will be randomized in a 2:1 ratio (30 subjects active:15 subjects placebo) for Treatment A (15 µg TAP-COVID-19 vaccine + 0.5 mg CpG) after Part A low dose has completed enrollment and received the first vaccination and the iSRC has reviewed safety data through Day 8.

Part B (50-85 years) high dose will be randomized in a 2:1 ratio (30 subjects active:15 subjects placebo) for Treatment B (45 µg TAP-COVID-19 vaccine + 0.5 mg CpG) after Part B low dose has completed enrollment and received the first vaccination and the iSRC has reviewed safety data through Day 8.

A total of 90 subjects will be randomized in Part A (18-49 years); 30 subjects low dose (Treatment A, 15 µg TAP-COVID-19 vaccine + 0.5 mg CpG), 30 subjects high dose (Treatment B, 45 µg TAP-COVID-19 vaccine + 0.5 mg CpG), and 30 subjects placebo (Treatment C).

A total of 90 subjects will be randomized in Part B (50-85 years); 30 subjects low dose (Treatment A, 15 µg TAP-COVID-19 vaccine + 0.5 mg CpG), 30 subjects high dose (Treatment B, 45 µg TAP-COVID-19 vaccine + 0.5 mg CpG), and 30 subjects placebo (Treatment C).

Treatment A: TAP-COVID-19 vaccine (15 µg) + CpG (0.5 mg) IM injection on Day 1 and Day 22 ( $\pm 3$  days)

CONFIDENTIAL

Treatment B: TAP-COVID-19 vaccine (45 µg) + CpG (0.5 mg) IM injection on Day 1 and Day 22 ( $\pm 3$  days)

Treatment C: Placebo (buffered saline solution) IM injection on Day 1 and Day 22 ( $\pm 3$  days)

A computer-generated randomization schedule for each part (Part A, Part B, and Part C Expansion) will be generated prior to study start by an ICON biostatistician.

For sentinel dosing, 3 subjects from each part will be randomized 2:1 (active:placebo). The remainder of each cohort will also be randomized 2:1 (active:placebo).

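### Section 6.7.1 advises against all vaccination for the study year, in conflict with criterion 23's influenza exception and inconsistent with criterion 24's 90-day limit and the planned approved-vaccine subsets

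*Combined protocol and SAP*

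**What the plan says.** Four parts of the protocol bear on vaccines received outside the study regimen.

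- **Section 6.7.1** tells subjects to refrain from "receiving vaccinations during study participation unless prescribed by the Investigator for treatment of specific clinical events". It sets no end date and names no vaccine. Section 4.1.1 puts participation at about 1 year.
- **Section 5.2, criterion 23** excludes anyone intending to have "another vaccine within the first 3 months of the study except influenza vaccine which should not be given within 2 weeks of study vaccine".
- **Section 5.2, criterion 24** excludes "Receipt of any other approved SARS-CoV-2 vaccine prior to the first study vaccine or within 90 days after administration of the first study vaccine". The lead-in to Section 5.2 lets the investigator discontinue a subject who comes to meet an exclusion criterion after entry, so both criteria can operate on study.
- **Sections 9 and 9.2** plan for receipt of such vaccines. Section 9 names a subset of "subjects that received an FDA Emergency Use Authorization/licensed COVID vaccine". Section 9.2 adds: "Subjects that are immunized with an approved vaccine will be captured as a subset analysis of the PP Population". That subset is to be formed by date of vaccination, for the visits on Days 90, 181, 273 and 365.

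The synopsis repeats criteria 23 and 24 in the same terms. Nothing in the documents says which rule prevails.

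**The concern.** An influenza or COVID-19 vaccine is given to prevent disease, so it does not naturally count as treatment of a clinical event. Read literally, 6.7.1 leaves no room for either during the whole year.

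The main stake is subject safety. Section 2.4 acknowledges that "Multiple vaccines have been approved for emergency use for the prevention of SARS-CoV-2". Section 6.6.2 provides that "Investigators, site staff, subjects, CRO [except for the unblinded team members preparing the data for unblinded iSRC review] will remain blinded until the completion" (meaning study end), so a placebo recipient does not know that he or she received no vaccine. Section 6.6.3.1 withdraws any subject whose code is released early. A subject who follows 6.7.1 may forgo an authorised vaccine long after criterion 24 has stopped barring it.

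The second stake is consistent handling by sites. Under 11.1.1, noncompliance with a protocol requirement is a deviation. Under 11.1, a deviation can lead to withdrawal or make a subject nonevaluable. An approved COVID-19 vaccine on Day 120 is contrary to 6.7.1, clear of criterion 24, and the very event that the 9.2 per-protocol subset is built to describe. A site cannot tell from the text how to classify it.

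**Working it through.** The plan gives no figure to reproduce. The check is a comparison of the rules with day counts, taking Day 1 as dose 1.

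**Inputs.** Dose 2 on Day 22 ±3, so Day 19 to 25 (Section 4.1.1). Influenza vaccine not within 2 weeks (14 days) of study vaccine, within the first 3 months (criterion 23). Bar of 90 days after dose 1 (criterion 24). Last visit on Day 365 ±14, so Day 351 to 379 (Table 1-1). Concomitant medication recorded through Day 43 (Section 6.7.1). Two assumptions: 3 months is taken as 90 days, ending on Day 1 + 90 = Day 91 (calendar months shift this by 1-2 days), and the 2-week rule applies on both sides of each dose.

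**Influenza vaccine, criterion 23 against 6.7.1.**

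- Between doses: dose 1 blocks through Day 1 + 14 = 15. Dose 2 blocks from Day 19 − 14 = 5, 22 − 14 = 8, or 25 − 14 = 11. These spans overlap, so no day between the doses is free.
- After dose 2: first free day = dose 2 day + 14 + 1.

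| Dose 2 | First free day | Days to Day 91 |
|---|---|---|
| Day 19 | 34 | 91 − 34 + 1 = 58 |
| Day 22 | 37 | 91 − 37 + 1 = 55 |
| Day 25 | 40 | 91 − 40 + 1 = 52 |

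On all of these days criterion 23 excepts influenza vaccine and 6.7.1 advises against it.

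**Approved COVID-19 vaccine, criterion 24 against 6.7.1.**

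- Last barred day: 1 + 90 = Day 91. First day outside the bar: Day 92.
- Days 92 to 365: 365 − 92 + 1 = 274, and 274/365 = 75%.
- Across the visit window: 351 − 92 + 1 = 260, to 379 − 92 + 1 = 288.

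On these days no exclusion criterion bars the approved vaccine and the analysis plan expects some receipt, while 6.7.1 still advises against it.

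**Capture of the vaccination date.** The 9.2 subset is defined by that date. Concomitant medication recording stops at Day 43, and the first day outside criterion 24 comes 92 − 43 = 49 days later. Table 1-1 does schedule medical-history updates at Days 90, 181, 273 and 365, but the text does not say that vaccinations are recorded there.

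**The case against.** The strongest reply is that the COVID-19 half shows no contradiction. Section 6.7.1 is worded as advice (should, not must), is not an exclusion criterion, and states no consequence. Criterion 24 does carry one: a vaccine on Day 60 meets the criterion and may lead to discontinuation under 5.2, while one on Day 120 does not. The two can coexist as an enforceable bar through Day 91 and advice throughout. This stands. A reader might infer that the 90-day limit has no effect if 6.7.1 governs the year; discretionary discontinuation gives it effect, so that inference fails. What remains is an inconsistency: the plan stops enforcing a bar and prepares for receipt, yet keeps advising against the vaccine with no stated reason.

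A reader might also take the planned subsets as proof that later vaccination is permitted. They are not, since a plan may summarise events that it discourages. They show only that receipt was expected.

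On influenza, criterion 23 concerns plans at entry and is the more specific rule, so many sites would follow it. That softens the practical effect, but the two texts still give opposite guidance on the same days.

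On harm, subjects may withdraw without prejudice (5.6) and need not know their assignment to seek a vaccine. The consent form is not among the documents reviewed, so what subjects were told about authorised vaccines is unknown. The effect is therefore discouragement, not denial.

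**Conclusion.** The point holds as a conflict in the instructions on influenza vaccine (52 to 58 days, ending on Day 91) and an inconsistency on approved COVID-19 vaccine (Days 92-365, 274 days; 260 to 288 across the final visit window). The counts rest on Day 1 as dose 1 and, for influenza, on 3 months read as 90 days. The sentence should be corrected for the sake of subjects' safety and clear site instructions.

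Two larger conclusions are tempting and not supported.

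- *That 60 placebo recipients of 180 are affected, 30 of them aged 50-85.* Those are the planned numbers in 9.3 (30 per part, 30 + 30 = 60). The Amendment 8 summary of changes states that enrolment has stopped and no more subjects will be added. The people concerned are those still in follow-up. Their number is not given, and few or none may still fall in the influenza window.
- *That the trial's results are compromised.* The primary endpoint is solicited reactions in the 7 days after each dose, nominally ending on Day 29, and all analysis is descriptive. Immunogenicity summaries use the mITT population (9.6), which does not exclude subjects for deviations. A deviation label could affect per-protocol membership and hence the 9.2 subset, but not the primary result.

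**What to change.** 1. Amend the 6.7.1 sentence to except (i) influenza vaccine not given within 2 weeks of study vaccine and (ii) an approved or emergency-authorised COVID-19 vaccine more than 90 days after dose 1.
2. State in 6.7.1 that the date and product of any such vaccine are recorded through Day 365, for example at the existing medical-history updates. Without this, accepting later vaccination could remove the deviation record as a source of the date that the 9.2 subset needs.
3. Send sites a clarification covering subjects still in follow-up.

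Leave the 9.2 subset unchanged, including Day 90, because it separates early recipients whether or not they complied with criterion 24.

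The cost is a short amendment with IRB approval, a letter to sites, and a small amount of added data entry. No new subjects or visits are needed. The downside is that more subjects may receive an approved vaccine before the Day 181, 273 and 365 immunogenicity visits, leaving fewer whose titres reflect study vaccine alone. The planned subset separates them, provided that the dates are recorded.

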### **6.7.2 Other Restrictions**

Subjects will be instructed to adhere to the following restrictions:

- Strenuous activity (as assessed by the Investigator) is prohibited from 48 hours prior to the days safety laboratory blood will be collected
- Subjects are not permitted to consume alcohol for 3 days prior to vaccination and should refrain from consumption of alcohol until 7 days post vaccination.
- Subjects should refrain from blood donation for 6 months post vaccination.
- Subjects should not participate or plan to participate in a study that involves an experimental agent (vaccine, drug, biologic, device, or medication); or should not have received an experimental agent within 1 month before enrollment in this study; or who expect to receive another experimental agent during participation in this study.

## **7 STUDY ASSESSMENTS AND PROCEDURES**

Subjects will undergo study procedures and assessments at time points specified in the Schedule of Assessments and Procedures ([Table 1-1](#)).

### **7.1 Pandemic Safety Procedures**

Appropriate measures will be taken to ensure the safety of both study staff and study subjects including social distancing and appropriate personal protective equipment.

### **7.2 Medical and Surgical History**

The Investigator or designee will collect a complete medical and surgical history at screening. Medical and surgical history will be collected at CRU visits to determine if any changes have occurred since screening.

### **7.3 Demographic Characteristics**

Demographic characteristics including sex, age, race, and ethnicity will be recorded. Tobacco use and history will also be documented.

### **7.4 Physical Measurements**

Height (cm) and body weight (kg) without shoes will be recorded. BMI will be calculated using the height obtained at screening.

### **7.5 Immunogenicity**

Blood samples for antibody titers will be collected per [Table 1-1](#) to assess:

- Vaccine (ELISA for IgM and IgG, total antibody) and neutralizing antibody titers (virus microneutralization) for each treatment group:
  - GMT ratio (GMTplacebo/GMTTAP-COVID-19)
  - Seroconversion rate is defined as the proportion of subjects at the respective time point that have detectable antibodies (IgG and IgM) against SARS-CoV-2 Spike Protein RBD following challenge with vaccine (and potentially by natural asymptomatic or symptomatic infection by the virus in case of a placebo subject).
- Anti-RBD and anti-Fc antibodies

Blood samples for cellular immunity (PBMCs) will be collected per [Table 1-1](#). The numbers of cytokine producing CD4+ and CD8+ T-cells from PBMCs responsive to vaccine antigens will be analyzed using a validated procedure.

PBMC and serum samples for future research will also be collected (5-7 aliquots [1 mL]) at the time points outlined in [Table 1-1](#).

Immunogenicity sample collection, processing, and shipping details will be outlined in a separate SRM.

CONFIDENTIAL

## 7.6 SARS-CoV-2 Exposure and Asymptomatic Monitoring

Subjects will be monitored for SARS-CoV-2 exposure for potential asymptomatic infection throughout the study. CRU staff will interview subjects about any potential exposure to the virus. If a subject has had potential exposure, the CRU will perform an unscheduled nasopharyngeal swab. Subjects will not be discontinued from the study due to positive SARS-CoV-2 test results.

- If a subject has a positive or borderline ELISA anti-N IgG result, sites should have the subject return for an unscheduled PCR. If the ELISA is positive and the PCR is negative, the sites should follow the subjects using the standard of care under Investigator discretion, retesting ELISA at the next study visit(s) or sooner (per the Investigator's decision).
- If the subject has a positive or borderline ELISA anti-N IgG AND a positive PCR test, the clinical sites should bring the subjects back for repeat PCR testing as described below.
- The clinical sites should continue to collect PCR tests if a subject is experiencing possible COVID-19 symptoms, or had possible exposure to SARS-CoV-2 (ie, close contact tests positive for SARS-CoV-2). Testing will occur every 2 weeks for a total of 4 weeks (if 2 consecutive negative tests) or until negative (x2) after a positive result. Positive results will be reported as an AESI ([Section 8.2.2](#)) and subjects followed for disease severity, duration, and outcome.

Telephone visits will be conducted to augment the in person visits through 6 months post-vaccination ([Table 1-1](#)). CRU staff will interview the subjects about any potential exposure to the virus. If a subject has had potential exposure, the CRU will ask the subject to come in for an unscheduled visit that will include a nasopharyngeal swab.

Subjects will be reminded at onsite visits and during telephone visits to contact the clinical site any time there is potential exposure to SARS-CoV-2 or they are experiencing any respiratory disease/symptoms suggestive of SARS-CoV-2 infection.

